#### 4.1.4. Handling of Missing and Incomplete Dates

In general, values for missing dates will not be handled unless methods for handling missing dates are specified in this section or relevant sections. The original reported dates collected on the eCRF should be used in all relevant listings. The following rules will be used for handling partial dates for analyses requiring dates.

When calculating the time since diagnosis of HS, a partial HS diagnosis date will be handled as follows in the calculation:

- If only the day is missing, then the first day of the month will be used.
- If both the month and day are missing, then 01 JAN of the year will be used.
- If the diagnosis date is completely missing, then the time since diagnosis will not be calculated.

When the date of the last dose is used in deriving variables such as duration of treatment or TEAE flag, a missing or partial date of the last dose will be handled as follows:

- If only the day is missing, then the earlier date of the last day of the month or the date that the participant discontinued treatment will be used.
- If both the month and day are missing, then the earlier date of 31 DEC of the year or the date that the participant discontinued treatment will be used.
- Otherwise, the date that the participant discontinued treatment will be used as the date of the last dose.

For response endpoints, all nonresponders, as well as all participants who are missing postbaseline values, will be defined as nonresponders for the NRI analysis.

For continuous endpoints, any participant who is missing postbaseline values may have missing data handled using MMRM under the missing-at-random assumption. Mixed model repeated measures implicitly adjusts for missing data through a variance-covariance structure.

For other endpoints, missing observations will be handled as detailed in the specific sections addressing each analysis.

## 4.2. Variable Definitions

The following variables will only be calculated if not reported on the eCRF.

### 4.2.1. Body Mass Index

Body mass index will be calculated as follows:

BMI  $(kg/m^2) = [weight (kg)] / [height (m)]^2$ .

### 4.2.2. Prior and Concomitant Medication

Prior medication is defined as any nonstudy medication started before the first dose of INCB054707 or placebo in the PC period.

In the PC period, concomitant medication is defined as any nonstudy medication that is started accordingly:

- Before the date of first administration of INCB054707 or placebo in the PC period and is ongoing throughout the study or ends on/after the date of first study drug administration during the PC period.
- On/after the date of first administration of INCB054707 or placebo in the PC period and is ongoing or ends during the PC period.

In the OLE period, concomitant medication is defined as any nonstudy medication that is started accordingly:

- Before the date of first administration of INCB054707 75 mg in the OLE period and is ongoing throughout the study or ends on/after the date of first study drug administration during the OLE period.
- On/after the date of first administration of INCB054707 75 mg in the OLE period and is ongoing or ends during the OLE period.

In the LTE period, concomitant medication is defined as any nonstudy medication that is started accordingly:

- Before the date of first administration of INCB054707 in the LTE period and is ongoing throughout the study or ends on/after the date of first study drug administration during the LTE period.
- On/after the date of first administration of INCB054707 in the LTE period and is ongoing or ends during the LTE period.

A prior medication could also be classified as "both prior and concomitant medication" if the end date is on or after first dose of INCB054707 or placebo. In the listing, it will be indicated whether a medication is only prior, only concomitant, or both prior and concomitant.

For the purposes of analysis, all medications will be considered concomitant medications unless the medications can unequivocally be defined as not concomitant.

## 5. STATISTICAL METHODOLOGY

### 5.1. General Methodology

Unless otherwise noted, SAS® software (SAS Institute Inc, Cary, NC; v9.1 or later) will be used for the generation of all tables, graphs, and statistical analyses. Descriptive summaries for continuous variables will include but not be limited to the number of observations, mean, standard deviation, median, minimum, and maximum. Descriptive summaries for categorical variables will include the number and percentage of participants in each category.

## 5.2. Treatment Groups

This is a randomized, double-blind, placebo-controlled, dose-ranging study followed by an open-label extension period, and an optional long-term extension period. Table summaries, unless otherwise indicated, will present data by treatment groups. The results will be summarized and presented separately for the PC period, the OLE period, and the LTE period, unless otherwise specified.

For the PC period, the treatment groups will be placebo and INCB054707 15 mg, 45 mg, and 75 mg.

For the OLE period, the participants will be grouped into the following groups according to the treatment group they received during the PC period:

- Placebo to INCB054707 75 mg
- INCB054707 15 mg to 75 mg
- INCB054707 45 mg to 75 mg
- INCB054707 75 mg

For the LTE period, the participants will be grouped into the following groups according to the initial INCB054707 dose group they received in the LTE period:

- INCB054707  $\leq$  45 mg
- INCB054707  $\ge$  60 mg

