Study Design	This is a Phase 2, multicenter, parallel group, placebo-controlled, double-blind, randomized study to evaluate the efficacy and safety of INCB054707 (15, 45, and 75 mg QD) over a 16-week treatment period. Upon completion of the 16-week treatment period, participants will continue for 36 weeks of open-label INCB054707 treatment (75 mg QD). At the end of the OLE, all eligible participants will have the option to continue treatment for additional 48 weeks in an LTE period, to collect long-term safety and efficacy data for a total of 104 weeks. A safety follow-up visit will be conducted approximately 4 weeks after the last dose of study drug.
Estimated Duration of Study Participation	Up to 30 days for screening, followed by continuous treatment in the placebo-controlled period for 16 weeks, followed by a 36-week OLE period, an optional 48-week LTE period, and then a 28-day safety follow-up visit. It is estimated that an individual will participate for approximately 14 months (without the LTE period), or approximately 25 months if participating in the LTE period.
DMC	Yes (internal)
Coordinating Principal Investigator	[name] [name], MS, MEd

Table 2:Key Study Design Elements (Continued)

Treatment Groups and Duration:

The study design is shown in Figure 1. The SoA is detailed in Table 3.

Figure 1: Study Design Schema

After providing informed consent, participants will be assessed for study eligibility at the screening visit. Participants will undergo screening within 30 days prior to randomization. Participants who continue to meet eligibility criteria at baseline will undergo Day 1 (Week 0) assessments and be randomized to 1 of 4 treatment groups. Participants will be stratified based on geographical region (North America and outside of North America) and disease severity (Hurley Stages I, II, and III) with no more than 25% of the total number of participants as Hurley Stage III.

Approximately 200 participants will be randomized 1:1:1:1 to receive double-blinded study treatment of placebo or 1 of 3 doses of INCB054707 (15, 45, or 75 mg) PO QD for 16 weeks. At Week 16, participants will enter the 36-week OLE period (INCB054707 75 mg QD). At the

CONFIDENTIAL

completion of the OLE period, Week 52 visit, eligible participants may enter the 48-week LTE period. A safety follow-up visit will be scheduled approximately 4 weeks after the end of the OLE period (Week 56 visit) or the LTE period (Week 104 visit).

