APPENDIX D. PROTOCOL AMENDMENT SUMMARY OF CHANGES

Document	Date
Amendment 1	10 SEP 2021

Amendment 1 (10 SEP 2021)

Overall Rationale for the Amendment:

The primary purpose of the amendment is to obtain additional long-term safety and efficacy data through 104 weeks; and to incorporate changes from country-specific amendments for Germany (dated 04 DEC 2020) and Canada (dated 08 MAR 2021). Additional changes are summarized below.

 Section 1, Protocol Summary (Table 2: Key Study Design Elements; Table 3: Schedule of Activities); Section 2.1.2, Scientific Rationale for Study Design; Section 2.1.3, Justification of Dose; Section 2.2.2, Benefit Assessment; Section 3, Objectives and Endpoints (Table 5: Objectives and Endpoints); Section 4.1, Overall Design; Section 4.2, Overall Study Duration; Section 6.1, Study Treatments Administered (Table 6: Study Treatment Information); Section 6.3, Measures to Minimize Bias: Randomization and Blinding; Section 6.5.1, Criteria and Procedures for Dose Interruptions and Adjustments of Study Drug; Section 6.6.2, Restricted Medication and Procedures; Section 6.6.4.2, Number of Rescue Interventions; Section 6.7, Treatment After the End of the Study; Section 7.1.2, Discontinuation Procedures; Section 7.2, Participant Withdrawal From the Study; Section 8.7, End of Treatment and/or Early Termination

Description of change: At the completion of the 36-week OLE period (preceded by the 16-week placebo-controlled period), all eligible participants will have the option to continue treatment for an additional 48 weeks (LTE period), followed by a 4-week safety follow-up period.

Rationale for change: To obtain additional long-term safety and efficacy data through 104 weeks.

4. Section 2.1.4, Justification for Placebo

Description of change: Added Section 2.1.4, Justification for Placebo.

Rationale for change: Per request made by the Germany's Health Authority to provide a rationale for a placebo arm in this HS study.

5. Section 2.1.5, Justification for Doses in the Long-term Extension

Description of change: Added Section 2.1.5, Justification for Doses in the Long-term Extension.

Rationale for change: To provide a rationale for the long-term extension and the doses available in that period.

6. Section 5.1, Inclusion Criteria

Description of change: Added Inclusion Criterion 6.

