## **1. INTRODUCTION**

This is a Phase 2, multicenter, parallel group, placebo-controlled, double-blind, randomized study to evaluate the efficacy and safety of INCB054707 (15, 45, and 75 mg QD) over a 16-week PC period. Upon completion of the 16-week PC period, participants will continue for 36 weeks of OLE period (INCB054707 75 mg QD). At the end of the OLE period, all eligible participants have the option to continue treatment for additional 48 weeks in an LTE period, to collect long-term safety and efficacy data for a total of 104 weeks. A safety follow-up visit will be conducted approximately 4 weeks after the last dose of study drug.

The purpose of this SAP is to provide details of the statistical analyses that have been outlined in the Study INCB 54707-204 Protocol.

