#### 4.1.3. Baseline Value

Baseline is the last nonmissing measurement obtained before the first administration of INCB054707 or placebo in the PC period, unless otherwise defined.

For randomized participants not treated with any study drug, baseline is defined as the last nonmissing assessment before or on the day of randomization for all parameters.

For participants who continue in the OLE period, baseline is defined as follows:

- For efficacy evaluation, baseline is the last nonmissing measurement obtained before the first administration of study drug in the PC period, unless otherwise defined.
- For safety evaluation in the OLE period:
  - For participants who cross over from the placebo group or the INCB054707 15 or 45 mg groups to INCB054707 75 mg, baseline is the last nonmissing measurement obtained before the first administration of INCB054707 75 mg in the OLE period.
  - For participants who take INCB054707 75 mg throughout study participation up to Week 52, baseline is the last nonmissing measurement obtained before the first administration of study drug in the PC period.

For participants who continue in the LTE period, baseline is defined as follows:

- For efficacy evaluation, baseline is the last nonmissing measurement obtained before the first administration of study drug in the PC period, unless otherwise defined.
- For safety evaluation in the LTE period, baseline is the last nonmissing measurement obtained before the first administration of INCB054707 in the LTE period.

When scheduled assessments and unscheduled assessments occur on the same day and the time of the assessment or time of first dose is not available, use the following convention to determine baseline:

- If both a scheduled and an unscheduled visit are available on the day of the first dose and the time is missing, use the scheduled assessment as baseline.
- If all scheduled assessments are missing on the day of the first dose and an unscheduled assessment is available, use the unscheduled assessment as baseline.

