#### 9.2.2. Adverse Event Summaries

AE will be summarized by treatment groups for the safety population in the PC period, the open-label evaluable population in the OLE period, participants who take INCB054707 75 mg throughout study participation up to Week 52, and the long-term evaluable population in the LTE period.

An overall summary of AEs will include the following:

- Number (%) of participants reporting any TEAEs
- Number (%) of participants reporting any serious TEAEs
- Number (%) of participants reporting any Grade 3 or higher TEAEs
- Number (%) of participants reporting any treatment-related TEAEs
- Number (%) of participants who temporarily interrupted study treatment because of TEAEs
- Number (%) of participants who permanently discontinued study treatment because of TEAEs
- Number (%) of participants who had a fatal TEAE

The following summaries will be produced by MedDRA term (if 10 or fewer subjects appear in a table, a listing may be appropriate):

- Summary of TEAEs by MedDRA SOC and PT
- Summary of TEAEs by MedDRA PT in decreasing order of frequency
- Summary of TEAEs by MedDRA SOC, PT, and maximum severity
- Summary of TEAEs by MedDRA SOC, PT, and CTCAE grade category
- Summary of Grade 3 or higher TEAEs by MedDRA SOC and PT
- Summary of Grade 3 or higher TEAEs by MedDRA PT in decreasing order of frequency
- Summary of serious TEAEs by MedDRA SOC and PT
- Summary of serious TEAEs by MedDRA PT in decreasing order of frequency
- Summary of treatment-related TEAEs by MedDRA SOC and PT
- Summary of treatment-related TEAEs by MedDRA PT in decreasing order of frequency
- Summary of Grade 3 or higher treatment-related TEAEs by MedDRA SOC and PT

- Summary of treatment-related serious TEAEs by MedDRA SOC and PT
- Summary of TEAEs with a fatal outcome by MedDRA SOC and PT
- Summary of TEAEs leading to dose reduction by MedDRA SOC and PT
- Summary of TEAEs leading to dose interruption by MedDRA SOC and PT
- Summary of TEAEs leading to discontinuation of study drug by MedDRA SOC and PT
- Summary of TEAEs requiring concomitant medications by MedDRA SOC and PT

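### Adverse events are reported only as crude percentages over unequal periods, and no readable summary joins the long-term extension to earlier exposure

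*SAP*

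**What the plan says.** Protocol Table 2 gives the purpose of the long-term extension (LTE): "to collect long-term safety and efficacy data for a total of 104 weeks". The rationale for Amendment 1 in Protocol Appendix D says the same: "to obtain additional long-term safety and efficacy data through 104 weeks".

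SAP 5.2 sets the default layout: "The results will be summarized and presented separately for the PC period, the OLE period, and the LTE period". The sentence goes on to allow exceptions specified elsewhere. LTE participants are grouped by their initial LTE dose (45 mg or less, 60 mg or more), not by randomized arm.

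SAP 9.2.2 applies the adverse event (AE) tables to four sets: the placebo-controlled (PC) period, the open-label extension (OLE), participants on 75 mg throughout up to Week 52, and the LTE. Every line of the overall summary is a count and percentage, beginning with "Number (%) of participants reporting any TEAEs".

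SAP 9.2.1 restarts the treatment-emergent window at the first dose of each period. It ends the window at the first dose of the next period, or at the end of safety follow-up. SAP 4.1.3 resets the safety baseline at LTE entry. SAP 6.4 summarizes treatment duration for the same four sets, but no readable AE table uses it as a denominator.

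**The concern.** A crude percentage depends on how long participants were observed. Here the windows differ two- to threefold in length, only the first has a control, and dropout shortens them further. Side by side, the columns invite a comparison that they cannot support.

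The extensions exist to provide long-term safety data. Yet the readable plan has no table showing how many participants ever had a given event between first INCB054707 dose and the end of follow-up, or at what rate per unit of exposure. Uncommon events would be spread over ten active-drug columns: three PC, four OLE, one Week 52 and two LTE.

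**Working it through.** **1. The plan's own figure.** 16 + 36 + 48 = 100 weeks of treatment, plus about 4 weeks of follow-up (SAP section 1: "A safety follow-up visit will be conducted approximately 4 weeks after the last dose of study drug"), gives 104 weeks. The figure reproduces. The windows are not exactly 16, 36 and 48 weeks, because a participant who does not enter the next period adds about 4 weeks.

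**2. Effect of window length alone.** Assume a constant hazard and a 16-week risk p. Then P(t) = 1 − (1 − p)^(t/16). The values of p are assumptions, as the documents give no event rates for this study.

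| 16 wk | 36 wk | 48 wk | 36/16 ratio | 48/16 ratio | 104 wk |
|---|---|---|---|---|---|
| 2.0% | 4.4% | 5.9% | 2.22 | 2.94 | 12.3% |
| 5.0% | 10.9% | 14.3% | 2.18 | 2.85 | 28.4% |
| 10.0% | 21.1% | 27.1% | 2.11 | 2.71 | 49.6% |
| 20.0% | 39.5% | 48.8% | 1.97 | 2.44 | 76.6% |
| 40.0% | 68.3% | 78.4% | 1.71 | 1.96 | 96.4% |

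An exposure-adjusted rate would be flat along each row. No readable table gives the quantity in the last column.

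**3. With dropout.** Add exponential dropout of d per year, g = −ln(1 − d)/52 per week, with h = −ln(1 − p)/16. The observed percentage is h/(h + g) × [1 − exp(−(h + g)t)]. For p = 10%:

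- d = 10%: 9.8%, 20.4% and 25.9% over 16, 36 and 48 weeks.
- d = 40%: 9.3%, 17.9% and 21.9%.

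The growth shrinks but does not disappear.

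**4. Reach of the Week 52 summary.** Take about 50 per arm (SAP 3.1), no dropout and full LTE entry, with a 52-week year. Active-drug person-years are:

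- PC: 150 × 16/52 = 46.
- OLE: 200 × 36/52 = 138.
- LTE: 200 × 48/52 = 185.
- Total: 369, a ceiling.

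The 75 mg arm to Week 52 contributes 50 × 52/52 = 50. That is 50/369 = 14% of the total, or 50/185 = 27% of active exposure up to Week 52 (46 + 138, or 185 before rounding).

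**5. Can the columns be added?** No. Under SAP 9.2.1, a participant with a new event in the PC period and another in the OLE counts in both. The Week 52 column also overlaps the 75 mg PC and OLE columns. The sum is therefore not the number ever affected.

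**6. Who is in the Week 52 group?** SAP 4.1.3 places it ("For participants who take INCB054707 75 mg throughout study participation up to Week 52") under the rules for participants who continue into the OLE, which can be read as continuers only. SAP Tables 2 and 3 start it at the first 75 mg dose in the PC period, end it at the last dose up to Week 52, and require no OLE dose. Membership is not settled in the readable text.

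**The case against.** Several points on the other side are sound.

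- **Cross-period summary.** A reader of section 5.2 alone might infer that nothing crosses the periods. That is wrong: the sentence allows exceptions, and section 9.2.2 plans a full AE summary for 75 mg up to Week 52.
- **The 104-week purpose.** It describes data collection. The visible safety endpoint is the frequency and severity of AEs, which counts and grades address. Much of the objectives table is blacked out, so one cannot say that a stated 104-week endpoint goes unanswered.
- **Unseen text.** SAP Appendix A, the list of displays, is not shown, and the contents list has a blank entry after 5.3.5. A reader might infer that no population or cumulative table exists. The documents do not establish that.
- **Direction.** It is tempting to say that period length will look like rising risk. That needs a constant hazard. Protocol 2.2.1 reports platelet decreases that were transient and stabilized, and three of four arms change treatment at Week 16. Later percentages could fall. This limits the direction of the distortion; it does not make the columns comparable.
- **Early stoppers.** Even if the Week 52 group were continuers only, the AEs of participants who stopped 75 mg early would not be hidden. They appear in the PC safety-population tables.
- **Separate periods are sensible.** They keep controlled and open-label data apart, treatment duration is shown for the same sets, and listings carry all AEs. This argues for keeping the by-period tables. Duration summaries alone give neither an event rate nor a count of participants ever affected.

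**Conclusion.** The point holds in a limited form. In the readable SAP, AEs are crude percentages over windows of unequal length. The only cross-period summary covers one arm and ends at Week 52, reaching about 14% of the maximum active exposure. Nothing readable links LTE events to earlier exposure. Window length alone could change a percentage by a factor of 1.7 to 2.9, given a constant hazard and 16-week risks of 2% to 40%. The person-year figures assume no dropout and full LTE entry.

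This is an inexpensive improvement to reporting. It is not an error in the trial's conduct or in its primary analysis, and it lapses to the extent that the unseen Appendix A already contains such displays.

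**What to change.** In SAP 9.2.2, keep the existing number (%) tables and add:

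1. For the overall AE categories in each period, exposure-adjusted incidence rates: participants with the event per 100 person-years at risk, with 95% confidence intervals.
2. One all-INCB054707 summary from first INCB054707 dose (the first OLE dose for the placebo arm) to the end of safety follow-up, overall and by original arm, counting each participant once per event term.

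In SAP 5.3, state that the 75 mg up to Week 52 group includes everyone with at least one 75 mg dose in the PC period, and align 4.1.3 with that.

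If Appendix A already lists such tables, a cross-reference in 9.2.2 is enough.

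The cost is SAP wording and a few tables from dates already collected. The rates assume roughly constant risk, and the pooled summary mixes 15 and 45 mg with later 75 mg and LTE doses. The crude by-period tables should therefore stay beside them.

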### 5.3. Analysis Populations

#### 5.3.1. Intent-to-Treat Population

All participants who were randomized to the study constitute the ITT population. Treatment groups for this population will be defined according to the treatment assignment at the time of randomization regardless of the actual study treatment the participant might apply during his/her participation in the PC period.

The ITT population will be used for the summary of demographics, baseline characteristics, participant disposition, and analyses of all efficacy data in the PC period.

#### 5.3.2. Per Protocol Population

Participants in the ITT population who are considered to be sufficiently compliant with the Protocol compose the PP population. The determination of participants being considered for exclusion from the PP population by the clinical team will be prepared and signed before unblinding and database lock.

The PP population will be used in the supportive sensitivity analysis for the primary efficacy endpoint.

